7.2.3.1 Analytical method

[figure not shown]
The plasma samples from all patients will be assayed for LDK378 concentrations, using a validated liquid chromatography-tandem mass spectrometry assay (LC-MS/MS). Values below the lower limit of quantification (LLOQ) of approximately 1.0 ng/mL or lower will be reported as 0.00 ng/mL. Missing values will be labeled accordingly.

7.2.5 Resource utilization

Direct collection of health care resource utilization (HCRU) data (such as occurrences of hospitalization) is not planned for this study, but may be explored based on data contained within the SAEs eCRF.

8 Safety monitoring and reporting

8.1 Adverse events

8.1.1 Definitions and reporting

An adverse event is defined as the appearance of (or worsening of any pre-existing) undesirable sign(s), symptom(s), or medical condition(s) that occur after patient's signed informed consent has been obtained.

Abnormal laboratory values or test results occurring after informed consent constitute adverse events only if they induce clinical signs or symptoms, are considered clinically significant, require therapy (e.g., hematologic abnormality that requires transfusion or hematological stem cell support), or require changes in study medication(s).

Adverse events that begin or worsen after informed consent should be recorded in the Adverse Events CRF. Conditions that were already present at the time of informed consent should be recorded in the Medical History page of the patient's CRF. Adverse event monitoring should be continued for at least 30 days (or 5 half-lives, whichever is longer) following the last dose of study treatment. Adverse events (including lab abnormalities that constitute AEs) should be described using a diagnosis whenever possible, rather than individual underlying signs and symptoms. When a clear diagnosis cannot be identified, each sign or symptom should be reported as a separate Adverse Event.

Adverse events will be assessed according to the Common Terminology Criteria for Adverse Events (CTCAE) version 4.03 (dated 14 June 2010). If CTCAE grading does not exist for an adverse event, the severity of mild, moderate, severe, and life-threatening, corresponding to Grades 1 - 4, will be used. CTCAE Grade 5 (death) will not be used in this study; rather, information about deaths will be collected through a Death eCRF.

Abnormal laboratory values or test results occurring after signing the ICF constitute adverse events only if they induce clinical signs and symptoms, or require therapy, (e.g., any hematologic abnormality that requires transfusion of hematological stem cell support) or changes in medication(s) are considered clinical significant and should be recorded on the Adverse Event eCRF under signs, symptoms or diagnosis associated with them. In addition, isolated abnormal laboratory values that are considered clinical significant (e.g. cause study discontinuation or constitute in and of itself a Serious Adverse Event) should be recorded on the Adverse Events eCRF.

The occurrence of adverse events should be sought by non-directive questioning of the patient (subject) during the screening process after signing informed consent and at each visit during the study. Adverse events also may be detected when they are volunteered by the patient (subject) during the screening process or between visits, or through physical examination, laboratory test, or other assessments. As far as possible, each adverse event should be evaluated to determine:

- The severity grade (CTCAE Grade 1-4)
- Its duration (Start and end dates)
- Its relationship to the study treatment (Reasonable possibility that AE is related: No, Yes)
- Action taken with respect to study or investigational treatment (none, dose adjusted, temporarily interrupted, permanently discontinued, unknown, not applicable)
- Whether medication or therapy was given (no concomitant medication/non-drug therapy, concomitant medication/non-drug therapy)
- Outcome (not recovered/not resolved, recovered/resolved, recovering/resolving, recovered/resolved with sequelae, fatal, unknown)
- Whether it is serious, where a serious adverse event (SAE) is defined as in [Section 8.2.1](#)

All adverse events should be treated appropriately. If a concomitant medication or non-drug therapy is given, this action should be recorded on the Adverse Event CRF.

Once an adverse event is detected, it should be followed until its resolution or until it is judged to be permanent, and assessment should be made at each visit (or more frequently, if necessary) of any changes in severity, the suspected relationship to the study treatment, the interventions required to treat it, and the outcome.

Progression of malignancy (including fatal outcomes), if documented by use of appropriate method (for example, as per RECIST criteria for solid tumors or as per Cheson's guidelines for hematological malignancies), should not be reported as a serious adverse event.

Adverse events separate from the progression of malignancy (example, deep vein thrombosis at the time of progression or hemoptysis concurrent with finding of disease progression) will be reported as per usual guidelines used for such events with proper attribution regarding relatedness to the drug.

8.1.2 Laboratory test abnormalities

8.1.2.1 Definitions and reporting

Laboratory abnormalities that constitute an Adverse event in their own right (are considered clinically significant, induce clinical signs or symptoms, require concomitant therapy or require changes in study treatment), should be recorded on the Adverse Events CRF. Whenever possible, a diagnosis, rather than a symptom should be provided (e.g. anemia instead of low hemoglobin). Laboratory abnormalities that meet the criteria for Adverse Events should be followed until they have returned to normal or an adequate explanation of the abnormality is found. When an abnormal laboratory or test result corresponds to a sign/symptom of an already reported adverse event, it is not necessary to separately record the lab/test result as an additional event.

Laboratory abnormalities, that do not meet the definition of an adverse event, should not be reported as adverse events. A Grade 3 or 4 event (severe) as per CTCAE does not automatically indicate a SAE unless it meets the definition of serious as defined below and/or as per investigator's discretion. A dose hold or medication for the lab abnormality may be required by the protocol in which case the lab abnormality would still, by definition, be an adverse event and must be reported as such.

8.1.3 Adverse events of special interest

Details regarding these adverse events are provided in the [Investigator's Brochure] for ceritinib. Potential emergent new AEs will be monitored during the course of the study.

8.2 Serious adverse events

8.2.1 Definitions

Serious adverse event (SAE) is defined as one of the following:

- Is fatal or life-threatening
- Results in persistent or significant disability/incapacity
- Constitutes a congenital anomaly/birth defect
- Is medically significant, i.e., defined as an event that jeopardizes the patient or may require medical or surgical intervention to prevent one of the outcomes listed above
- Requires inpatient hospitalization or prolongation of existing hospitalization,
- Note that hospitalizations for the following reasons should not be reported as serious adverse events:
 - Routine treatment or monitoring of the studied indication, not associated with any deterioration in condition
 - Elective or pre-planned treatment for a pre-existing condition that is unrelated to the indication under study and has not worsened since signing the informed consent
 - Social reasons and respite care in the absence of any deterioration in the patient's general condition
- Note that treatment on an emergency outpatient basis that does not result in hospital admission and involves an event not fulfilling any of the definitions of a SAE given above is not a serious adverse event

8.2.2 Reporting

To ensure patient safety, every SAE, regardless of suspected causality, occurring after the patient has provided informed consent and until at least 30 days after the patient has stopped study treatment must be reported to Novartis within 24 hours of learning of its occurrence.

Any SAEs experienced after this 30 days period should only be reported to Novartis if the investigator suspects a causal relationship to the study treatment. Recurrent episodes, complications, or progression of the initial SAE must be reported as follow-up to the original episode within 24 hours of the investigator receiving the follow-up information. An SAE occurring at a different time interval or otherwise considered completely unrelated to a previously reported one should be reported separately as a new event.

Information about all SAEs is collected and recorded on the Serious Adverse Event Report Form; all applicable sections of the form must be completed in order to provide a clinically thorough report. The investigator must assess and record the relationship of each SAE to each specific study treatment (if there is more than one study treatment), complete the SAE Report Form in English, and send the completed, signed form by fax within 24 hours to the oncology Novartis Drug Safety and Epidemiology (DS&E) department.

The telephone and telefax number of the contact persons in the local department of Drug Safety and Epidemiology (DS&E), specific to the site, are listed in the investigator folder

provided to each site. The original copy of the SAE Report Form and the fax confirmation sheet must be kept with the case report form documentation at the study site.

Follow-up information is sent to the same contact(s) to whom the original SAE Report Form was sent, using a new SAE Report Form stating that this is a follow-up to the previously reported SAE and giving the date of the original report. Each re-occurrence, complication, or progression of the original event should be reported as a follow-up to that event regardless of when it occurs. The follow-up information should describe whether the event has resolved or continues, if and how it was treated, whether the blind was broken or not, and whether the patient continued or withdrew from study participation.

If the SAE is not previously documented in the [Investigator's Brochure] or Package Insert (new occurrence) and is thought to be related to the Novartis study treatment, an oncology Novartis Drug Safety and Epidemiology (DS&E) department associate may urgently require further information from the investigator for Health Authority reporting. Novartis may need to issue an Investigator Notification (IN), to inform all investigators involved in any study with the same drug that this SAE has been reported. Suspected Unexpected Serious Adverse Reactions (SUSARs) will be collected and reported to the competent authorities and relevant ethics committees in accordance with Directive 2001/20/EC or as per national regulatory requirements in participating countries.

8.3 Emergency unblinding of treatment assignment

Not applicable. This is an open-label study.

8.4 Pregnancies

To ensure patient safety, each pregnancy occurring while the patient is on study treatment must be reported to Novartis immediately (within 24 hours) of learning of its occurrence. Patients who become pregnant during the trial must be withdrawn. The pregnancy will be followed up from the estimated date of delivery plus 3 months to determine outcome, including spontaneous or voluntary termination, details of the birth, and the presence or absence of any birth defects, congenital abnormalities, or maternal and/or newborn complications.

Pregnancy should be recorded on a Clinical Trial Pregnancy Form and reported by the investigator to the oncology Novartis DS&E. Pregnancy follow-up should be recorded on the same form and should include an assessment of the possible relationship to the investigational treatment of any pregnancy outcome. Any SAE experienced during pregnancy must be reported on the SAE Report Form.

Pregnancy outcomes must be collected for the female partners of any males who took study treatment. A pregnancy outcome informed consent will be provided by Novartis. Consent to report information regarding these pregnancy outcomes should be obtained from the mother.

Women of childbearing potential should be advised to use highly effective contraception methods while they are receiving study treatment and up to 3 months after treatment has been stopped.

If a pregnancy occurs while on study treatment, the newborn will be followed for at least 3 months.

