8. Major surgery (e.g., intra-thoracic, intra-abdominal or intra-pelvic) within 4 weeks prior (2 weeks for resection of brain metastases) to starting study drug or who have not recovered from side effects of such procedure. Video-assisted thoracic surgery (VATS) and mediastinoscopy will not be counted as major surgery and patients can be enrolled in the study ≥ 1 week after the procedure.
9. Patients receiving treatment with medications that meet one of the following criteria and that cannot be discontinued at least 1 week prior to the start of treatment with LDK378 and for the duration of the study (see Appendix I):
 - Strong inhibitors or strong inducers of CYP3A4/5
 - Medications with a low therapeutic index that are primarily metabolized by CYP3A4/5, and/or CYP2C9
 - Medication with a known risk of prolonging the QT interval or inducing Torsades de Pointes
10. Impairment of GI function or GI disease that may significantly alter the absorption of LDK378 (e.g., ulcerative diseases, uncontrolled nausea, vomiting, diarrhea, or malabsorption syndrome).
11. Patients who are currently receiving treatment with warfarin sodium (Coumadin®) or any other coumarin-derivative anticoagulants.
12. Patients receiving unstable or increasing doses of corticosteroids. If patients are on corticosteroids for endocrine deficiencies or tumor-associated symptoms, (other than CNS-related), dose must have been stabilized (or decreasing) for at least 5 days before first dose of study treatment.
13. Patients receiving treatment with any enzyme-inducing anticonvulsant that cannot be discontinued at least 1 week before first dose of study treatment, and for the duration of the study. Patients on non enzyme-inducing anticonvulsants are eligible.
14. Investigational agents within 4 weeks or $\leq 10 \times$ half-life of the agent (whichever is longer) before first dose of study treatment.
15. Pregnant or nursing (lactating) women, where pregnancy is defined as the state of a female after conception and until the termination of gestation, confirmed by a positive hCG laboratory test.

16. Women of child-bearing potential, defined as all women physiologically capable of becoming pregnant, **unless** they are using highly effective contraception during the study and for 3 months after stopping LDK378 treatment. Highly effective contraception is defined as any of:

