- Total abstinence: when this is in line with the preferred and usual lifestyle of the patient. [Periodic abstinence (e.g., calendar, ovulation, symptothermal, post-ovulation methods) and withdrawal are not acceptable methods of contraception].
- Sterilization: have had surgical bilateral oophorectomy (with or without hysterectomy) or tubal ligation at least six weeks before taking study treatment. In case of oophorectomy alone, only when the reproductive status of the woman has been confirmed by follow up hormone level assessment.
- Male partner sterilization (at least 6 months prior to screening) (With the appropriate post-vasectomy documentation of the absence of sperm in the ejaculate). (For female patients on the study the vasectomized male partner should be the sole partner for that patient).
- Use of a **combination** of any two of the following (a+b or a+c or b+c):
 - a. Use of oral, injected or implanted hormonal methods of contraception that have comparable efficacy (failure rate < 1%), for example hormonal vaginal ring or transdermal hormone contraception.
 - b. Placement of an intrauterine device (IUD) or intrauterine system (IUS)
 - c. Barrier methods of contraception: Condom or Occlusive cap (diaphragm or cervical/vault caps) with spermicidal foam/gel/film/cream/vaginal suppository.

In case of use of oral contraception women should have been stable on the same pill for a minimum of 3 months before taking study treatment.

Women are considered post-menopausal and not of child bearing potential if they have had 12 months of natural (spontaneous) amenorrhea with an appropriate clinical profile (e.g., age appropriate, history of vasomotor symptoms) or have had surgical bilateral oophorectomy (with or without hysterectomy) or tubal ligation at least six weeks prior to screening. In the case of oophorectomy alone, only when the reproductive status of the woman has been confirmed by follow up hormone level assessment is she considered not of child bearing potential.

17. Sexually active males must use a condom during intercourse while taking the drug and for 3 months after stopping LDK378 treatment and should not father a child in this period. A condom is required to be used also by vasectomized men in order to prevent delivery of the drug via seminal fluid.

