7.2.2.5.4 Pregnancy and assessments of fertility

During screening, a serum pregnancy test will be completed (Day -28 to Day -1). On cycle 1 Day 1 prior to dosing and at subsequent cycles and at EOT, urinary pregnancy test (dipstick) will be performed. The time windows granted for pregnancy testing are identical to the corresponding visit time windows for each visit. Refer to [Table 7-1](#). If local requirements dictate otherwise, local regulations should be followed.

Women who are determined not to be of child bearing potential before the study will only be tested at screening. When non-child bearing potential status is determined during the study, further pregnancy testing will not be continued. Women are considered post-menopausal if they have had 12 months of natural (spontaneous) amenorrhea with an appropriate clinical profile (e.g. age appropriate, history of vasomotor symptoms), and otherwise not of child bearing potential if they have had surgical bilateral oophorectomy (with or without hysterectomy) or tubal ligation at least six weeks ago. In the case of oophorectomy alone, only when the reproductive status of the woman has been confirmed by follow up hormone level assessment is she considered not of child bearing potential (such testing is not covered

as part of the study assessments). If local requirements dictate otherwise, local regulations should be followed.

The time windows granted for pregnancy testing are identical to the corresponding visit time windows for each visit. Refer to [Table 7-1](#). If a positive pregnancy test is performed in between study visits, the patients must immediately notify the investigator.

Male patient must notify the investigator in case their partner is resulted pregnant during the treatment period.

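### Pregnancy reporting, newborn follow-up and partner notification are explicit only for the treatment period, although contraception is required for 3 months after the last dose and other wording in Section 8.4 is wider

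*Protocol*

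**What the plan says.** **Duties limited to treatment.** Protocol Section 8.4 opens with the rule that "each pregnancy occurring while the patient is on study treatment must be reported to Novartis immediately (within 24 hours" of learning of it). It closes with: "If a pregnancy occurs while on study treatment, the newborn will be followed for at least 3 months". Section 7.2.2.5.4 says: "Male patient must notify the investigator in case their partner is resulted pregnant during the treatment period". On testing, that section says that "at subsequent cycles and at EOT, urinary pregnancy test (dipstick) will be performed". Section 4.1 places the EOT visit within 7 days of the last dose.

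**Contraception beyond treatment.** Exclusion criterion 16 (Section 5.3) excludes women of child-bearing potential unless they are "using highly effective contraception during the study and for 3 months after stopping LDK378 treatment". Criterion 17 requires condom use by sexually active men during treatment and "for 3 months after stopping LDK378 treatment and should not father a child in this period". Section 8.4 repeats the advice to women: contraception "while they are receiving study treatment and up to 3 months after treatment has been stopped".

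**Wider wording in Section 8.4.** The same section also says: "Pregnancy outcomes must be collected for the female partners of any males who took study treatment". It gives no time limit there. It requires withdrawal of patients who become pregnant in the course of the trial, and the next sentence has the pregnancy followed to its outcome. The sentences on recording a pregnancy on the Pregnancy Form, and on reporting SAEs that arise in pregnancy, carry no time limit either.

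**The concern.** The protocol asks patients to avoid conception for 3 months after stopping the drug. The duties that would make a conception in that period known to the sponsor are spelled out only for the time on drug. Where one section states its period in several ways, sites will apply it differently, and the narrowest reading is the one in the reporting sentence itself.

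What is at stake is safety information: whether a pregnancy conceived shortly after the last dose is reported within 24 hours, followed to outcome, and the newborn followed. For partners of male patients the problem is more specific. Outcome collection is mandatory, but the only notification that could start it is limited to the treatment period.

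**Working it through.** The plan gives no figure to reproduce. The check sets the stated periods side by side and measures the interval between them.

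| Provision | Place in protocol | Period stated | Reaches past the last dose? |
|---|---|---|---|
| 24-hour pregnancy report | 8.4, first sentence | on treatment | no |
| Newborn follow-up | 8.4, last sentence | on treatment | no |
| Partner notification | 7.2.2.5.4 | treatment period | no |
| Scheduled pregnancy test | 7.2.2.5.4 | up to EOT | at most 7 days |
| Contraception, women | 5.3 (16); 8.4 | to 3 months after stopping | yes |
| Contraception, men | 5.3 (17) | to 3 months after stopping | yes |
| Withdrawal, then outcome follow-up | 8.4 | during the trial | yes, if read with 7.1.5 |
| Pregnancy Form | 8.4 | none | open |
| Partner outcomes | 8.4 | none | yes, but nothing triggers it |

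Section 7.1.5 counts a patient as on the study while in efficacy or survival follow-up. That is why the withdrawal sentence can be read as reaching past the last dose.

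**Length of the window.** SAP Section 4.1.5 sets a month at 30.4375 days, so 3 × 30.4375 = 91.3 days. The explicit pregnancy-reporting sentence covers none of them.

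**What general safety reporting covers.** Section 8.1.1 monitors adverse events for at least 30 days or 5 half-lives, whichever is longer. The longest single-dose half-life in Section 1.2.1.2.4 is 48 h, and 5 × 48 = 240 h = 10 days, so 30 days governs. The accumulation ratio of 6.2 in that section gives a longer effective half-life: 24 × ln 2 / −ln(1 − 1/6.2) = about 95 h. Five of these make about 20 days, still under 30. The remainder is 91.3 − 30 = 61.3 days. Section 8.2.2 requires every SAE to be reported for at least 30 days after treatment, and after that only if the investigator suspects causality. Section 8.2.1 lists a birth defect as an SAE criterion but not pregnancy itself.

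**Existing contacts.** Survival contacts are every 12 weeks in Section 7.1.7.3 (every 3 months in Section 4.1). A contact 12 weeks after the last dose falls on day 84, and 91.3 − 84 = 7.3 days before the window closes. Section 4.1 starts these contacts only once tumor follow-up has ceased. Patients who stop without progression have 8-weekly tumor visits instead. Neither contact alone serves every patient.

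**The case against.** The strongest reply is that Section 8.4 is wider than its opening sentence. Withdrawal and outcome follow-up are tied to the trial, which under Section 7.1.5 includes survival follow-up. The Pregnancy Form sentence is untimed, and partner outcomes are required for any man who took the drug. Other routes exist too. Section 7.2.2.5.4 asks for immediate notification of a positive test between visits. Section 14.2.4.3 lists pregnancy as a reason for ending post-treatment follow-up. A birth defect remains reportable as an SAE after 30 days if causality is suspected. The visible text is also incomplete: a redacted block follows the contraception paragraph in Section 11.3, Table 7-1 survives only in part, and the consent and pregnancy forms are separate documents.

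Much of this stands. A reader might infer that pregnancies after the last dose fall outside reporting and follow-up altogether. The documents do not support that, because the wider sentences can be read to include them. What the reply does not supply is any visible sentence that expressly carries the 24-hour report, partner notification or newborn follow-up into the 3 months. The Pregnancy Form sentence may simply describe how to file the on-treatment reports required just before it. A patient's duty to tell the investigator does not by itself oblige the site to report to the sponsor.

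**Conclusion.** The point holds as an internal conflict. Three explicit duties end with treatment, contraception runs about 91 days longer, and other wording in Section 8.4 fits neither limit cleanly. A site could reasonably read that it has no reporting duty in that interval. For about 61 of those days unconditional SAE reporting has also lapsed.

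Two further inferences should be avoided. The protocol requires contraception for 3 months; it does not call that interval a defined period of fetal risk. And the 66 of 103 patients off treatment on 29-Sep-2015 (Amendment 3 rationale) are not the number at risk. They are all discontinuations, whatever the reason and regardless of child-bearing potential, and the figure does not show who was still within 3 months of the last dose.

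The number at risk and the expected number of pregnancies are not given; the latter is likely small. No efficacy or PK analysis is affected. The conclusion rests on the visible text and on the SAP's month length. It takes no view on how long contraception should last.

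**What to change.** Reconcile Sections 8.4 and 7.2.2.5.4 by stating one window for the 24-hour report, partner notification and newborn follow-up. It should run from first dose to the end of the protocol's existing 3-month post-treatment contraception period. Make the sentences on withdrawal and outcome follow-up, the Pregnancy Form and partner outcomes refer to that window, so that each duty has a trigger.

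Ask about pregnancy, in the patient or a partner, at the 30-day safety contact. Ask again at the first existing contact on or after the end of the 3 months, whether that is an 8-weekly tumor visit or a survival contact.

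The cost is a wording amendment, one added question at contacts already planned, and a few extra reports. The contraception period and all dosing rules stay as they are.
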